#### A1.1.1. Part B Long-Term Extension Phase: Overview/Rationale

Following Day 336/Week 48 and the completion of Part A (the Core Study Phase), any subject who, in the opinion of the investigator, is experiencing clinical benefit from pegcetacoplan administration will be invited to participate in Part B, the Long-Term Extension Phase, in order to continue to receive treatment with pegcetacoplan until it is commercially available for the disease under treatment.

During Part A Core Study Phase (up to Week 48), an acetate-buffered mannitol formulation of pegcetacoplan (pegcetacoplan 270 mg/day and 360 mg/day) will be used for daily SC dosing. At or after Week 24, at the discretion of the investigator, the subject can be transitioned to pegcetacoplan 1080 mg administered twice weekly by SC infusion using an acetate-buffered sorbitol formulation. At the time of entry into Part B, the Long-Term Extension Phase, subjects will be transitioned to the sorbitol formulation with pegcetacoplan 1080 mg administered twice weekly by SC infusion if they did not make this transition during Part A. In addition, subjects may transition to pegcetacoplan 1080 mg administered every 3 days (ie, a dose on every third day); see Section A1.1.3.2 for more details.

Table A1 provides the schedule of events for visits that will be conducted during the Part B Long-Term Extension Phase.

Table A1: Part B, Long-Term Extension Phase: Study Flow Chart (Week 48 and Beyond)

Study Period	I	ETF & ETE a						
		Dose Transition Visits b (Only for those who have not already transitioned to twice-weekly dosing)			Continue or Resume Regular Visits			
Study Week	48 b	T+1W	T+2W	T+4W	60	72	≥84 c	
Study Day	336 b	T+7D	T+14 D	T+28 D	420	504	588°	
Study Visit	15 b	T1	T2	T3	E16	E17	E≥18 c	
Visit Window (±Days)	2	2	2	2	7	7	7	NA
Physical examination d	X					X d		X
Triplicate 12-lead electrocardiogram e	X				X	X	X	Х

Table A1: Part B, Long-Term Extension Phase: Study Flow Chart (Week 48 and Beyond)

Study Period Long-Term Extension Phase: Week 48 and Beyond								
		Dose Transition Visits b (Only for those who have not already transitioned to twice-weekly dosing)			Continue or Resume Regular Visits			
Study Week	48 b	T+1W	T+2W	T+4W	60	72	≥84°	
Study Day	336 b	T+7D	T+14 D	T+28 D	420	504	588°	
Study Visit	15 b	T1	T2	Т3	E16	E17	E≥18 c	
Visit Window (±Days)	2	2	2	2	7	7	7	NA
$Pegceta coplan\ administration^{b,f}$	X	X	X	X	X	X	X	
Injection site assessment g	X	X	X	X	X	X	Х	
Concomitant medications	X	X	X	X	X	X	Х	X
Vital sign measurementsh	X	X	X	X	X	X	Х	X
Urine								
24-hour Urine Collection i	X					Xi	Xi	X
Dispense uPCR containers	X		X	X	X	X	Х	
Return uPCR samples j			X	X	X	X	Х	
Urinalysis—microscopic & Dipstick k	Х	Х	X	Х	X	Х	х	Х
Blood 								
Pharmacokinetic Sample Collection m	Х	Х	Х	Х	X	Х	х	Х
Antidrug Ab assays n	X			X		Х	X n	X
Hematology and chemistry 0,p	X	X	X	X	X	X	Х	X
PD for Complement profile	X	X	X	X	X	X	Х	X
Pregnancy (β-HCG and FSH)	X							
Disease-Specific Biomarkers	X							X
eGFR q	X							X
Urine pregnancy test r	X			X	X	X	Х	
Adverse events	X	X	X	X	X	X	х	Х
Drug Dispensation for Home Administration	X	Х	Х	Х	X	Х	Х	

Abbreviations: Ab = antibodies; ACR = albumin-to-creatinine ratio; ADA = antidrug antibody; ALP = alkaline phosphatase; ALT = alanine aminotransferase; aPTT = fibrinogen activated partial thromboplastin time; AST = aspartate aminotransferase; β-HCG = beta human chorionic gonadotropin; BUN = blood urea nitrogen; CKD-EPI = Chronic Kidney Disease Epidemiology Collaboration; ECG = electrocardiogram; eGFR = estimated glomerular filtration rate; ETE = Early Termination Exit Visit; ETF = Early Termination Follow-up Visit; FSH = follicle-stimulating hormone; GGT = gamma-glutamyl transferase; INR = international normalized ratio; LDH = lactate dehydrogenase; PCR = protein-to-creatinine ratio; PD = pharmacodynamics; PI = primary investigator; PK = pharmacokinetics; RBC = red blood cell(s); SC = subcutaneous;

uACR = urine albumin-to-creatinine ratio; uPCR = urine protein-to-creatinine ratio; WBC = white blood cell(s); WOCBP = women of childbearing potential.

- a Subjects who discontinue treatment early should complete one ETF 6 weeks after discontinuation of treatment and one ETE Visit 6 weeks after the ETF.
- b If subjects have not transitioned to twice-weekly dosing before entry into Part B, then transition visits T1, T2, and T3 need to be scheduled. Patients who had transitioned to twice-weekly dosing prior to entry into Part B may omit the Part B dose transition visits.
- c Following Extension Visit 18 (Week 84) subjects should continue to schedule visits at 12-week intervals (±7 days) until pegcetacoplan is commercially available for the disease under treatment.
- d A full physical examination should be performed at 24-week intervals (ie, at Week 48 and then every other visit starting at Week 72). Additional symptom-driven physical examinations may be performed at unscheduled time points if deemed necessary by the PI.
- e Triplicate 12-lead ECGs are to be performed before dosing and before blood sampling procedures.
- f Subjects will self-administer SC pegcetacoplan, after receiving appropriate training by a research nurse or other personnel. During site visits subjects will self-administer pegcetacoplan at the site if it occurs on a dosing day.
- g Between site visits, subjects will be instructed to report any injection site reaction to the study coordinator.
- h On clinic dosing days vital signs will be measured within 2 hours before dosing, venipuncture, and ECG assessments. On clinic dosing days, vital signs will be measured within 30 minutes after dosing.
- i 24-hour urine collected for ACR and PCR, defined as collection for a 24-hour period in a urine pooling container following the first urinary output on that day (first urinary output is discarded). Courier arrangements will be made by site personnel to pick up urine containers from patient's home. Urine ACR and PCR will be calculated on 24-hour urine collections for accuracy in estimating 24-hour proteinuria. Starting with the collection at Week 72, 24-hour urine collections will be every other visit (ie, every 24 weeks).
- j Urinary PCR samples (first urinary output for the day) should be collected on 3 consecutive days, biweekly, for both uACR/uPCR analysis with a ±3-day window. On weeks of scheduled clinic visits, samples will be brought with patient during the site visit. No biweekly uPCR collection will occur between extension visits, but 1 uPCR collection will occur halfway between each extension visit at the 6-week time point and will be picked up by courier.
- k Urinalysis—routine dipstick for protein, glucose, hemoglobin, blood, ketones, ACR, pH, bilirubin, urobilinogen, leukocyte esterase, specific gravity.
- 1 All blood samples will be taken predose.
- m All PK collections will be taken predose for treatment visits and following ECGs at all other visits. Predose PK collections to occur within 1 hour before dose. For subject visits falling outside of dosing schedule, PK samples can be taken following ECGs as mentioned for all other visits.
- n ADA samples should be collected at approximately 24-week intervals (ie, at Week 48 and then every other visit starting at Week 72). For subjects with positive ADA in last dose samples, additional samples of 6 and 12 months from last dose will be collected for further assessments.
- o Hematology consists of Hemoglobin, Hematocrit, RBC count, Platelet count, WBC count with differential (basophils, eosinophils, monocytes, lymphocytes, neutrophils), aPTT, INR. The use of silica reagents in coagulation panels should be avoided in subjects treated with pegcetacoplan.
- p Chemistry consists of BUN, Creatinine (b), Bilirubin (total and conjugated), Uric acid, Albumin, ALP, LDH, Creatine kinase, AST, ALT, GGT, Glucose, Sodium, Potassium, Chloride, Bicarbonate.
- q CKD-EPI creatinine equation (see https://www.niddk.nih.gov/); the CKD-EPI creatinine-cystatin C equation (if confirmation required).
- r Urine pregnancy test should be completed for WOCBP prior to dosing.

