#### 19. APPENDICES

# Appendix 1. Long-Term Extension Activities

## A1.1. Part B: Long-Term Extension Phase

This Appendix only contains information that is specific to the design and conduct of Part B, the Long-Term Extension Phase. Any processes, procedure, or information not described in this Appendix is identical to that described through the body of the main protocol.

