# A1.1.2. Part B Long-Term Extension Phase: Study Design and Procedures

Following Visit 15 (Week 48), subjects who elect to continue in Part B, the Long-Term Extension Phase, will return to the site at 12-week intervals until pegcetacoplan is commercially available for the disease under treatment.

Specific procedures for each visit are listed in the Study Flow Chart for the Long-Term Extension Phase in Table A1.

The vaccination history for each subject should be reviewed prior to entry into the Long-Term Extension Phase, and any additional vaccinations or boosters against *N. meningitidis*, *S. pneumoniae*, or *H. influenzae* as recommended in the Advisory Committee on Immunization

Practices (ACIP) guidelines for patients with immunocompromising conditions (available at https://www.cdc.gov/vaccines/schedules/hcp/imz/adult-conditions.html) should be provided. If additional vaccinations or boosters are required, vaccination titer samples should be collected before administration of the vaccination and at the next scheduled visit.

At Visit 15 (Week 48), subjects who are invited to participate in Part B, the Long-Term Extension Phase who have not already transitioned to 1080 mg twice-weekly pegcetacoplan treatment during Part A, will begin a pegcetacoplan dose regimen of pegcetacoplan 1080 mg twice weekly (with potential to escalate to pegcetacoplan 1080 mg every 3 days). Subjects should follow the Dose Transition visits as outlined in Table A1.

If a subject will initiate the pegcetacoplan 1080 mg twice weekly dose regimen at Visit 15, he or she should be instructed to skip their daily Part A Core Study Phase Dose the day prior to Visit 15 (ie, the subject should not self-administer pegcetacoplan on Day 335).

Subjects who discontinue treatment early should complete an Early Termination Follow-up Visit 6 weeks after discontinuation of treatment, and an Early Termination Exit Visit 6 weeks later as outlined in Table A1.

Study Assessments align with those conducted in the Core Study Phase and are described in Section 14.1.

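### Table A1 schedules no pregnancy test after the last dose for women who stop early in Part B; a urine test at the 6-week visit would cover the last interval on drug

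*Protocol*

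**What the plan says.** **Part B visits after an early stop.** Footnote a to Table A1 (protocol Appendix 1) reads: "Subjects who discontinue treatment early should complete one ETF 6 weeks after discontinuation of treatment and one ETE Visit 6 weeks after the ETF". Section A1.1.2 repeats this. No other general visit is scheduled after the stop.

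**Part B pregnancy testing.** Table A1 has two pregnancy rows.
- "Urine pregnancy test" is marked at Week 48, T3, E16, E17 and from E18 onward.
- The serum row is marked at Week 48 only.
- Both rows are blank in the shared column for the Early Termination Follow-up (ETF) and Early Termination Exit (ETE) visits.
- Footnote r reads: "Urine pregnancy test should be completed for WOCBP prior to dosing".
- Footnote c sets the spacing after E18: "subjects should continue to schedule visits at 12-week intervals".

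**Which text governs Part B.** Section A1.1 has a carry-over clause: "Any processes, procedure, or information not described in this Appendix is identical to that described through the body of the main protocol". Section A1.1.2 says: "Specific procedures for each visit are listed in the Study Flow Chart for the Long-Term Extension Phase in Table A1". It adds: "Study Assessments align with those conducted in the Core Study Phase and are described in Section 14.1".

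**Main protocol.**
- Inclusion criterion 7 (Section 11.1) requires contraception until 3 months after the last dose.
- Section 14.6 continues urine tests after treatment for subjects who enter the follow-up period, up to 12 weeks after the last dose at Visit 19.
- Section 13.4 gives Part A subjects who stop early and leave the study a visit at 6 weeks and the Exit Visit 6 weeks after that. The Exit Visit list in Section 13.4.1 has no pregnancy test.

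**The concern.** While a woman is being dosed in Part B, each interval between extension visits ends with a urine test. For a woman who stops between two visits, the last interval on drug does not. A pregnancy conceived in that interval meets no scheduled test, although she attends twice more and gives urine at both visits.

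What is at stake is the detection and follow-up of a pregnancy exposed to drug. Section 15.3 requires reporting within 24 hours and follow-up to outcome, but that duty starts only once the investigator is aware. Section 15.2 ends routine adverse-event collection at the exit or early termination visit.

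Section 6.4 gives some reason for care. Abortions and stillbirths increased in monkeys at 28 mg/kg/day, and the no-effect dose of 7 mg/kg/day is only about 1.3-fold above clinical exposure. The same section reports no effect on embryofetal development and says that the clinical relevance is unknown.

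**Working it through.** **1. Reading the column.** Table A1 has 20 procedure rows. In the ETF and ETE column, 13 are marked: physical examination, ECG, concomitant medications, vital signs, 24-hour urine, urinalysis, PK, antidrug antibodies, hematology and chemistry, PD, disease-specific biomarkers, eGFR and adverse events. Seven are blank: drug administration, injection site, drug dispensation, two uPCR rows and the two pregnancy rows (13 + 7 = 20). The pregnancy rows have the same eight cells as neighboring rows that are marked in the last column, so the blanks are not an effect of text extraction. "24-hour Urine Collection" is among the marked rows.

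**2. Does the carry-over clause fill the blanks?** It imports only what Appendix 1 does not describe.
- Appendix 1 does describe pregnancy testing, in two rows and a footnote.
- Section A1.1.2 makes Table A1 the list of procedures for each visit.
- Section A1.1.2 points to Section 14.1, not to 14.6. Section 14.1.9.5 does list a serum pregnancy test, but Section 14.1.9 leaves timing to the Part A schedule.
- Section 14.6 is limited to subjects entering the follow-up period and ends at Visit 19, a Part A visit.

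The import is not clear, and a site working from Table A1 would not test.

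**3. Timing in Part B** (nominal days, visit windows ignored, stop date taken as the last dose).
- Extension visits: (420 − 336)/7 = 12, (504 − 420)/7 = 12 and (588 − 504)/7 = 12 weeks apart.
- A subject who changes regimen at Week 48 also has a test at T3 (4 weeks), so her next interval is 12 − 4 = 8 weeks. The 12-week interval applies to her from E16.
- Time on drug since the last test: 0 weeks if she stops at an extension visit, up to about 12 if she stops just before the next one.
- Last test to ETF: 0 + 6 = 6 up to 12 + 6 = 18 weeks.
- Last test to ETE: 0 + 12 = 12 up to 12 + 12 = 24 weeks.
- Scheduled tests after the last dose: 0.

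**4. Part A comparison.** The 12-week limit in Section 14.6 reproduces: Visit 19 is (420 − 336)/7 = 12 weeks after Week 48. Visit 18 is (378 − 336)/7 = 6 weeks after it.
- Full follow-up: urine tests at Visits 16 to 19, which include the 6-week and 12-week points.
- Stopped early and left the study: one follow-up visit at 6 weeks, then an Exit Visit with no pregnancy test. Table 1 is also blank at Visit 21. The count is at most 1.

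**5. Drug remaining at the two visits.** Section 7.1 gives effective half-lives of 8.0 days (PNH patients) and 10.1 days (healthy adults). I assume that this range applies here. Fraction remaining = 0.5^(days/half-life).
- ETF, day 42: 0.5^(42/8.0) = 2.6% and 0.5^(42/10.1) = 5.6%.
- ETE, day 84: 0.5^(84/8.0) = 0.07% and 0.5^(84/10.1) = 0.31%.

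**6. ETE and the contraception period.** Three calendar months are 89 to 92 days. ETE at day 84 falls 89 − 84 = 5 to 92 − 84 = 8 days before the end.

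**The case against.** Four arguments can be made for leaving the table as it is.

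- **Section 14.6 may already apply at ETF.** That visit is called a follow-up visit and falls within 12 weeks of the last dose, and the carry-over clause exists. This reading is possible, so a proven absence of testing cannot be claimed. It does not remove the ambiguity, because the table that sites work from is blank and its footnote points to dosing.
- **No rule is broken.** Criterion 7 sets a period for contraception, not for testing, and Part A testing itself ends before 3 months. This stands. A reader might infer that the protocol contradicts itself, but the documents show an omission only.
- **Part A early leavers are treated much the same.** This stands in part. A reader might set two tests in Part A (6 and 12 weeks) against none in Part B. That compares subjects in the full Part A follow-up with Part B early stoppers. On the matching early-exit pathway, Part A has at most one test and none at the exit. Section 13.5 does ask Part A subjects who stop treatment to attend all follow-up visits if they are willing and able, so some would be tested more often.
- **Other safeguards exist.** Physical examination, adverse events and concomitant medications are reviewed at ETF and ETE. Sections 13.4.2 and 14.1.9 allow unscheduled visits and tests, and Section 15.3 requires prompt reporting of a suspected pregnancy. These lower the risk, but they depend on someone suspecting a pregnancy or the subject reporting it.

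**Conclusion.** The point holds as a gap in the Part B schedule. For a woman of childbearing potential who stops early, Table A1 lists no pregnancy test after the last dose, and the main protocol does not clearly supply one. Up to about 12 weeks on drug may be followed by no scheduled test. This ceiling assumes nominal visit dates and a stop just before the next extension visit.

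ETF is the visit that matters most. It is the first after the last on-treatment test, and 2.6% to 5.6% of drug remains if the half-lives in Section 7.1 apply. The case for ETE is weaker. A reader might infer that a test there would close the contraception period, but it falls 5 to 8 days short. It would match the 12-week limit in Section 14.6 but not the Part A Exit Visit.

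The documents do not say how many women are affected. Table A3, which the amendment summary lists together with Table A1, was not in the text available to me and is unchecked. This is a minor safety precaution. No endpoint, analysis or sample-size figure depends on it.

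**What to change.** In Table A1, mark the urine pregnancy test at ETF for women of childbearing potential only, and extend footnote r to require it before dosing and at ETF. Because ETF and ETE share one column, the mark needs a note that it applies to ETF. The longest nominal wait between tests is then 18 weeks, and the last interval on drug ends with a test. If the sponsor meant Section 14.6 to apply, the same edit makes that plain.

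A test at ETE is optional. If it is added, add the same test to the Part A early-exit visit for consistency.

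The cost is a table mark and a footnote phrase in a protocol amendment, with sponsor agreement and IRB/IEC approval under Section 17.5. Each woman concerned has one urine test at an existing visit where urine is already collected. No new visit or blood sample is needed.

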# A1.1.2. Part B Long-Term Extension Phase: Study Design and Procedures

Following Visit 15 (Week 48), subjects who elect to continue in Part B, the Long-Term Extension Phase, will return to the site at 12-week intervals until pegcetacoplan is commercially available for the disease under treatment.

Specific procedures for each visit are listed in the Study Flow Chart for the Long-Term Extension Phase in Table A1.

The vaccination history for each subject should be reviewed prior to entry into the Long-Term Extension Phase, and any additional vaccinations or boosters against *N. meningitidis*, *S. pneumoniae*, or *H. influenzae* as recommended in the Advisory Committee on Immunization

Practices (ACIP) guidelines for patients with immunocompromising conditions (available at https://www.cdc.gov/vaccines/schedules/hcp/imz/adult-conditions.html) should be provided. If additional vaccinations or boosters are required, vaccination titer samples should be collected before administration of the vaccination and at the next scheduled visit.

At Visit 15 (Week 48), subjects who are invited to participate in Part B, the Long-Term Extension Phase who have not already transitioned to 1080 mg twice-weekly pegcetacoplan treatment during Part A, will begin a pegcetacoplan dose regimen of pegcetacoplan 1080 mg twice weekly (with potential to escalate to pegcetacoplan 1080 mg every 3 days). Subjects should follow the Dose Transition visits as outlined in Table A1.

If a subject will initiate the pegcetacoplan 1080 mg twice weekly dose regimen at Visit 15, he or she should be instructed to skip their daily Part A Core Study Phase Dose the day prior to Visit 15 (ie, the subject should not self-administer pegcetacoplan on Day 335).

Subjects who discontinue treatment early should complete an Early Termination Follow-up Visit 6 weeks after discontinuation of treatment, and an Early Termination Exit Visit 6 weeks later as outlined in Table A1.

Study Assessments align with those conducted in the Core Study Phase and are described in Section 14.1.

#### A1.1.3. Part B Long-Term Extension Phase: Dose Rationale

The rationale for the Part A pegcetacoplan dose regimen is provided in Section 8.2.

#### A1.1.3.1. Target Level of Pegcetacoplan Serum Concentration

The toxicological data accumulated from the animal studies were used to guide dose selection during the Phase 1 single ascending dose and multiple ascending dose studies in healthy volunteers (Study CCI). In particular, the highest doses were selected, based on exposure predicted by a PK model and compared with the exposures observed at the NOAEL in cynomolgus monkeys.

The planned twice-weekly dose of pegcetacoplan is 1,080 mg SC twice weekly, equivalent to 308 mg/day. Dose selection is based on past clinical experience with SC pegcetacoplan, coupled with nonclinical toxicological studies. Daily doses up to 360 mg/day have been tested in past and ongoing clinical trials, including this ongoing trial, and have been found to be well tolerated, with exposures that are well below the pegcetacoplan levels associated with the NOAEL in monkeys.

Using a target-mediated drug disposition pharmacokinetic/pharmacodynamic (PK/PD) model (Mager and Jusko, 2001), the relationship between dosing regimen and pegcetacoplan serum concentration is well-understood and well-predicted by the model. Figure A1 is the predicted PK profile for the dose of 1080 mg twice weekly (green line), compared to the NOAEL PK data observed in the pivotal 9-month chronic toxicological study in monkeys (Study 13CATX-004 [black line]). For comparison with previous human exposure, also included is the summary PK data from the ongoing PNH study, Study APL-CP0514 (270 mg/day cohort [blue line]), and healthy volunteer study, Study CCC at 360 mg/day (brown line) and 1300 mg biweekly (light blue line). Both studies demonstrated pegcetacoplan to be safe and well tolerated. The figure illustrates that the PK exposure at the dose of 1080 mg twice weekly should derive a PK

[figure not shown]
exposure slightly below that of 360 mg daily and should be safely below that observed at the NOAEL.

#### A1.1.3.2. Dosing Adjustment Option

Transition from 360 mg daily to 1080 mg twice weekly may result in a small decrease in exposure. Therefore, if an increase in proteinuria is observed upon transition to twice-weekly dosing, then an increase in dose to 1080 mg every 3 days may be considered, upon agreement with the sponsor. This amended dosing regimen will result in a higher PK exposure than that achieved with twice-weekly dosing. However, as illustrated in Figure A1, this increase in PK exposure (Cmax) will still be lower than that observed in Study (1300 mg twice weekly) and will still be safely below that observed at the NOAEL.

Any adjustment in dose will be discussed and confirmed in writing by the sponsor. In the event of a dose adjustment, proteinuria levels will be monitored biweekly (with unscheduled assessments, if necessary) for at least 4 weeks to assess the impact of the dose adjustment. In the event that the dose is adjusted, then a new dosing schedule will be established for that patient.

Figure A1: Observed and Predicted PK Profiles for Pegcetacoplan

Abbreviations: cyno = cynomolgus monkey; HV = healthy volunteer; NOAEL = no-observed-adverse-effect-level; PK = pharmacokinetic; PNH = paroxysmal nocturnal hemoglobinuria

Note: Predicted PK profiles for pegcetacoplan (green line) at the planned dose of 1,080 mg twice weekly, compared to the summary PK data at the NOAEL (13CATX-004 [black line]), ongoing PNH study APL-CP0514 270 mg/day cohort (blue line), and healthy volunteer study CCI for both the 360 mg/day (brown line) and 1,300 mg twice weekly cohorts (light blue line).

